In Parkinson's disease (PD), while motor disturbances are the predominant and most readily recognized symptoms, various non-motor symptoms frequently co-occur. Cognitive functions such as working memory and executive control are on average worse in PD, although with substantial variability across patients. This variability highlights the need for ongoing studies exploring the nature of cognitive deficits in PD and their relationship to disease severity and progression. This study utilizes pHMRI-measured dopamine buffering capacity in putative motor regions as a model of motor disease severity. We propose extending this approach to include measures of cognitive performance utilizing [the NIH Toolbox](#) [22]. The NIH Toolbox cognitive measures were chosen because they can be completed relatively quickly (important to minimize patient discomfort when assessed in the medication off state), because it incorporates tasks that directly assess functions known to be impaired in PD, and because of its recognized validity [23]. The hypothesis is that the extent of DA buffering capacity loss in pertinent regions (such as the caudate nucleus) will explain a significant fraction of the variance in specific cognitive abilities.

Secondary Aim

3. Test whether dopamine buffering capacity in caudate reflects severity of cognitive dysfunction.

STUDY DESIGN

Overall study timeline

The study is planned for complete enrollment within 3 years.

Overview of each subject's participation

After thorough clinical assessment on a screening visit, subjects return on a separate day for levodopa pHMRI. Clinical severity ratings are repeated. Regional CBF data from pre-specified brain VOIs (volumes of interest) are collected continually with ASL fMRI before levodopa, during a 10-minute i.v. loading dose, and then repeatedly over the next approximately 90 minutes.

Levodopa-naïve patients in Aim 2 will have all scan day procedures repeated identically on a second scan day after 6 ± 1 weeks of clinically dosed treatment with CD-LD.

Screening visit

1. Potential subjects will review a written informed consent document with the investigator or designee and will have opportunity to resolve questions or concerns. All procedures below are performed only after written documentation of consent.
2. We will collect the following measures at screening:
 - a. Basic demographic information
 - b. MRI safety checklist
 - c. Handedness (Edinburgh Handedness Inventory)

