3. Left and right caudate VOIs (LC, RC).
4. Left and right anterior putamen (LaP, RaP) as defined above. The nucleus accumbens is excluded.
5. Left and right nucleus accumbens (LNA, RNA).
6. Thalamus (Th).
7. Each voxel in the brain.

The primary analysis will be a correlation across all Aim 1 subjects of the k_e 's for a VOI to clinical measures of disease severity and duration. Duration of illness will be measured from the first symptom, as recorded on the screening day. Standard 20cm tapping speed in the L and R hand and hemi-UPDRS part III motor scores, both measured in the standard off condition, will capture the increased variance provided by clinical asymmetry and will be correlated with contralateral posterior putamen k_e . Midbrain k_e will be compared to total "off" UPDRS part III scores and tapping speed in the more affected hand. Specifically:

The primary comparisons for Aim 1 will be simple Pearson correlations:

1. between the off-period 20cm tapping speed in the more affected hand and the midbrain k_e , and
2. between the off-period total UPDRS part III motor score and the midbrain k_e .

Secondary comparisons for Aim 2 will be correlations:

3. between "off" 20cm tapping speed on each side and contralateral posterior putamen k_e , and
4. "off" hemi-UPDRS part III motor scores on each side and contralateral posterior putamen k_e .

For #3 and #4, we will calculate the r values using repeated measures correlation [24], with side as the repeated measure, rather than as $2n$ independent data points. However, we are interested in between-subject correlation as well as the within-subject r_{rm} that the `rmcorr` package focuses on, so we will also report that p value (corresponding to the first row in Table 3 of ref. [24]).

For Aim 2, the k_e 's for each VOI will be compared before and after 6 weeks of treatment in a repeated measures ANOVA analysis. Here the key comparison is whether k_e changes with time (before vs after treatment) in any VOI, controlling for side (more affected side vs less affected side). Our hypothesis is that this change with time is at or near 0, so our answer will be framed in terms of 95% confidence intervals for change. Any VOIs identified from the Aim 1 SPM analysis will also be tested.

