Secondary analyses will correlate k_e 's from secondary VOIs to all measures of disease severity (off tapping speed, off UPDRS III, disease duration) and to cognitive test scores (NIH Toolbox task scores adjusted for age), using the off-period scores for measures done on the scan day. Voxelwise analyses will use SPM with an initial threshold of $t \geq 3.0$ and statistical inference at the cluster level with a false discovery rate of 0.05. Another secondary analysis will use the k_e computed from the button box tapping speeds from the more affected hand and the levodopa concentrations, independent of the perfusion MRI data ("tapping k_e "). We will test whether the tapping k_e correlates with the k_e from the midbrain or contralateral posterior putamen, or other VOIs.

Note that we expect that k_e for some VOIs will correlate better than for other VOIs with measures of disease severity or duration. This conclusion is based on the expectation that a specific clinical effect may be better associated with dopamine buffering capacity in a specific (set of) brain region(s).

Therefore we expect that the k_e -vs-clinical slope may differ significantly from zero only for a subset of the VOIs; in other words, we do not expect the slopes to be parallel across VOIs, and therefore will not include all VOIs in a single ANCOVA with a factor for VOIs. However, any errors in estimating pharmacokinetic parameters (i.e., in reconstructing the continuous function $C_p(t)$, plasma levodopa concentration as a function of time for $t \geq 0$) occur at the subject level. Such errors will affect all k_e estimates for that subject (i.e., across all VOIs). Therefore we cannot assume independence across VOIs, within subject, for the measured estimates of k_e .

Visual analog scale (VAS) measures of side effects will be analyzed as repeated measures ANOVAs. Other variables (demographics, clinical measures, NIH Toolbox scores, etc.) will be summarized or compared as appropriate using standard statistical methods.

Additional analysis details

We will examine interactions of the key analyses with subject demographics or disease variables such as age or presence of dyskinesias.

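### Comparison 3 correlates left and right tapping with contralateral k_e without a hand-dominance term, although handedness is collected; prespecifying one is a cheap improvement

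*Combined protocol and SAP*

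**What the plan says.** Under STUDY DESIGN, Screening visit, item 2c of the measures collected is "Handedness (Edinburgh Handedness Inventory". Handedness is not mentioned again in the text available for review, and no eligibility criterion restricts it.

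In the Data analysis section, comparison 3 relates off-state "20cm tapping speed on each side and contralateral posterior putamen k_e". For comparisons 3 and 4 the plan states that "we will calculate the r values using repeated measures correlation [24], with side as the repeated measure", rather than treating the sides as independent points. It adds that "we are interested in between-subject correlation as well as the within-subject" correlation, so a between-subject p value is reported too. The stated reason for using both hands is that the side-specific measures "will capture the increased variance provided by clinical asymmetry".

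Two other provisions come close to the issue:

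- Additional analysis details: "We will examine interactions of the key analyses with subject demographics or disease variables such as age or presence of dyskinesias".
- The Aim 2 ANOVA of k_e before and after treatment: "controlling for side (more affected side vs less affected side".

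Neither names hand dominance.

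**The concern.** The within-subject part of comparison 3 uses only the difference between a subject's two hands. The plan wants that difference to reflect asymmetry of disease. If the dominant hand is also faster for non-disease reasons, the same difference carries a second component that nothing in the model removes. At best this is noise that lowers power in a sample of 20. If the contralateral k_e difference also has a systematic direction relative to dominance, it is bias, and could push r_rm towards or away from the hypothesised negative correlation. The variable needed to separate the two components is already collected.

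**Working it through.** **Inputs from the documents.** n = 20 (SAMPLE SIZE, Aim 1); threshold 0.05 and one-sided correlation hypotheses, negative for tapping speed (Additional analysis details); r = 0.5 as the planning effect (Power considerations).

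**Assumed inputs.** The r of 0.5 is carried over as the true within-subject |r|; 90% of subjects are right-handed; the dominance effect d and any k_e left-right offset o are varied over a range. Both d and o are in SD units of the respective side difference without that effect.

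**The plan's own figure.** The plan gives power above 80% at r = 0.5 and above 99% at r = 0.7, with no figure for comparison 3. A noncentral t with 18 df and noncentrality √n·r/√(1−r²) gives √20 × 0.5/√0.75 = 2.58, hence 79.9% one-sided; at r = 0.7 it gives 99.5%. That is in line with the stated figures. Simulating a bivariate-normal Pearson correlation gives 75.4% and 97.9%.

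**Step 1: what r_rm is with two sides.** Let Dy be the right-minus-left tapping difference and Dx the matching difference in contralateral k_e. A common slope with one intercept per subject reduces to a regression of differences through the origin:

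r_rm = ΣDx·Dy / √(ΣDx² · ΣDy²), error df = 40 − 20 − 1 = 19.

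**Step 2: add a dominance effect.** Write Dy = β·Dx + d·h + e, with h = +1 for right-handers and −1 for left-handers. The mean square of Dy rises from 1 to 1 + d². If Dx is unrelated to h, r_rm shrinks by about 1/√(1+d²): a factor of 0.97, 0.89 and 0.71 at d = 0.25, 0.5 and 1.0. A true 0.5 becomes about 0.485, 0.447 and 0.354.

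**Step 3: power.** Simulated with true |r| = 0.5, no k_e offset, and affected side unrelated to dominance:

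| d (SD) | As planned, 19 df | With dominance term, 18 df |
|---|---|---|
| 0 | 77.5% | about 76% |
| 0.1 | 77.1% | about 76% |
| 0.2 | 75.8% | about 76% |
| 0.25 | 74.9% | about 76% |
| 0.5 | 67.6% | about 76% |
| 1.0 | 47.9% | about 76% |

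The two analyses break even near d = 0.2.

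**Step 4: type I error.** With true r = 0 and no k_e offset it is 5% at every d. An offset o gives a spurious mean r of about (2×0.9 − 1)·o·d / √((1+o²)(1+d²)). At d = 0.5 and o = −0.5 this is −0.2/1.25 = −0.16. A negative offset means lower k_e opposite the right hand. Simulated one-sided error at d = 0.5:

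| k_e offset −/+ (SD) | As planned | With term |
|---|---|---|
| 0 | 5% | 5% |
| 0.1 | 7% / 4% | 5% |
| 0.25 | 10% / 2% | 5% |
| 0.5 | 17% / 1% | 5% |

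The second route is an association between dominance and the more affected side. If the dominant side is the more affected one with probability 0.4 or 0.6, error at d = 0.5 is 9.1% or 2.6% (mean r_rm −0.07 or +0.07), and about 5% with the term.

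**Step 5: the between-subject result.** A constant dominant-hand advantage shifts every subject's two-hand mean by the same amount, so it drops out of the between-subject correlation.

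**The case against.** The strongest objection is that the premise lies outside the documents. They show that handedness is measured. They do not show that the dominant hand is faster on a 60-second task with keys 20 cm apart, in the off state, in this disease. That stands, so every figure here is conditional. Below about 0.2 SD the added term costs slightly more power than it saves.

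A reader might infer that comparison 3 runs at a type I error of 17%. The documents do not support that. It needs a 0.5 SD dominance effect together with a 0.5 SD left-right offset in posterior putamen k_e, and nothing in the plan suggests such an offset; the same anatomical rule defines both putamina. With no offset, and with affected side unrelated to dominance, the error is 5%.

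A reader might also infer that the whole asymmetry question is compromised. It is not. The between-subject result is reported and essentially unaffected, and comparison 4 examines the same asymmetry with hemi-UPDRS rather than tapping. The weight of comparison 3 is itself unclear: the Data analysis section lists it as secondary, while Additional analysis details counts it among four numbered primary analyses.

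Finally, the promised interactions are open-ended and could include handedness. That helps little: a subject-level interaction does not by itself remove an offset between a subject's two hands. The Aim 2 side factor concerns k_e, and more versus less affected side rather than dominance.

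**Conclusion.** The omission is confirmed, and the mechanism is correct for the method named. It is an optional refinement of one analysis, not an error that invalidates it.

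Under the stated assumptions, leaving dominance out costs about 8 points of power at 0.5 SD (68% against 76%) and about 28 at 1.0 SD (48% against 76%). At 0.25 SD the two analyses are almost level. Bias in r_rm needs a further condition, either a k_e offset or a link between dominance and affected side, and can go in either direction. The size of the dominance effect, any k_e offset, the share of right-handers and the within-subject r of 0.5 are all assumptions. The case for acting is the imbalance: a small, known cost against a possibly large loss, using a baseline value already in hand.

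**What to change.** Prespecify for comparison 3 the same within-subject ANCOVA (subject factor, common slope on contralateral posterior putamen k_e) with one added term for dominant versus non-dominant hand, taken from the Edinburgh score. State the coding in advance: either the sign of the score, or the continuous score, so that mixed-handed subjects need no cutoff. Report the adjusted within-subject r on 40 − 20 − 2 = 18 error df beside the planned r_rm, and leave the between-subject p value as it is.

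The cost is one degree of freedom: about 2 points of power if dominance has no effect, or about 3 if the dominant side is the more affected one with probability 0.4 or 0.6. No new data or procedures are needed. With 20 subjects, the choice is more credible if fixed before the tapping and k_e data are examined.

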predict variance of the key outcome measures and provide a formal power analysis. We have chosen the sample sizes here pragmatically, to allow recruitment and scanning at a steady, practically achievable rate. We note that the sample size of 20 for Aim 1 provides power >80% to find a moderately strong positive correlation ($r = 0.5$) while maintaining a low false positive rate $\alpha=0.05$. Power exceeds 99% to find a very strong correlation that would explain half the variance in disease severity ($r = 0.7$).

Additional levodopa-naïve subjects would not help Aim 1 substantially, as a Pearson correlation analysis is not appropriate if a large fraction of subjects are lumped at one end of the range of disease duration or severity. Therefore we plan to limit to 2 the number of subjects included in both Aims. However, if severity or duration vary substantially among the never-treated subjects, we may include more than two of them in the Aim 1 analysis. The number of subjects for Aim 2 is largely pragmatic, given the difficulty of recruitment and the additional cost with 2 scans per subject.

INCLUSION CRITERIA

There are two groups of subjects. All have idiopathic Parkinson disease. For the first group, we will attempt to sample a broad range of severity and disease duration. The second group will not be treated currently with levodopa, so most subjects in this group will be early in the disease process.

Inclusion criteria for all subjects:

- Age 40-79 at screening
- Meet accepted diagnostic criteria for Parkinson disease

EXCLUSION CRITERIA

Exclusion criteria for all subjects:

- Pregnancy
- Metal in the head or eye, or other contraindication to MRI
- Deep brain stimulator (DBS)
- Patients taking a dopamine antagonist or dopamine partial agonist
- Claustrophobia
- Significant neurologic disease other than PD (exceptions would include febrile seizures or uncomplicated migraine)
- Head trauma with loss of consciousness for more than 5 minutes
- Severe or unstable systemic illness
- MMSE < 24
- History of a primary psychotic disorder
- Current severe major depressive episode (clinical diagnosis after psychiatric interview)
- Current alcohol use disorder (clinical diagnosis after screening with the Michigan Alcoholism Screening Test)
- Current psychosis
- Subjects who feel that going without nicotine for 3-4 hours would be uncomfortable
- Currently taking an extended-release formulation of a dopamine agonist

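### Comparisons #3 and #4 (posterior putamen) are headed Aim 2 (N = 10) although they belong to Aim 1 (N = 20), are labelled both secondary and primary, and have no written between-subject estimate

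*Combined protocol and SAP*

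**What the plan says.** **Population.** In Analysis Plan, Data analysis, the lead paragraph on correlations begins "The primary analysis will be a correlation across all Aim 1 subjects". It then says that left and right tapping speed and hemi-UPDRS will be related to contralateral posterior putamen k_e. The numbered list follows. #1 and #2 (midbrain) are the primary comparisons for Aim 1. The heading over #3 and #4 (posterior putamen) reads "Secondary comparisons for Aim 2 will be correlations". The Aim 2 analysis starts only after that, and it is of another kind: the k_e values "will be compared before and after 6 weeks of treatment in a repeated measures ANOVA analysis". Specific Aim 1 names midbrain and posterior putamen and 20 patients. Sample Size gives N = 20 for Aim 1 and N = 10 for Aim 2.

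**Tier.** Data analysis labels #1 and #2 primary and #3 and #4 secondary. Additional analysis details refers to all four numbered analyses as primary, says they will not be corrected for multiplicity, and calls the secondary analyses exploratory. Posterior putamen is listed among the primary VOIs.

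**Estimator.** For #3 and #4, "we will calculate the r values using repeated measures correlation [24"], with side as the repeated measure. The plan adds that "we are interested in between-subject correlation" as well as in the within-subject r_rm, and continues "so we will also report that p value (corresponding to the first row in Table 3 of ref. [24"]). It writes out no between-subject coefficient, confidence interval or model. Additional analysis details does give the direction: one-sided, positive for UPDRS and negative for tapping speed.

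**The concern.** Posterior putamen is one of the two regions on which Aim 1 rests, and #3 and #4 are where its test is specified. An analyst who follows the heading would run both tests in the levodopa-naïve group. Inclusion Criteria says of that group "so most subjects in this group will be early in the disease process", and Sample Size warns that "a Pearson correlation analysis is not appropriate if a large fraction of subjects are lumped at one end of the range" of duration or severity. That warning is the plan's own reason for limiting overlap between the groups. The smaller and probably narrower sample affects both the between-subject result and r_rm.

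The tier label decides whether a positive putamen result is reported as primary or secondary evidence, and how many uncorrected tests make up the primary family.

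The estimator matters because r_rm and the between-subject correlation answer different questions. Whether patients with worse disease have higher posterior putamen k_e is a between-subject question, and for that the plan commits only to a p value that a reader must find in another paper.

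**Working it through.** **Inputs from the documents.** N = 20 (Aim 1) and N = 10 (Aim 2); one-sided 0.05; two sides per subject; r = 0.5 and 0.7 from the power paragraph. Those r values were stated for the Aim 1 Pearson correlation. Applying them to #3 and #4 is an assumption, because the plan gives no power for these comparisons.

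**1. The plan's own figures.** Sample Size claims power above 80% at r = 0.5 and above 99% at r = 0.7 with N = 20. One-sided noncentral t with a fixed predictor, df = N − 2 and noncentrality √N · r/√(1 − r²), gives 79.9% and 99.5%, so both reproduce within rounding. Bivariate-normal simulation, with both variables random, gives about 75% and 98%. The simulated values are used below.

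**2. Population, between-subject Pearson r.** Critical r = t/√(t² + df), df = N − 2.
- N = 20: t = 1.734, df 18, critical r = 0.38.
- N = 10: t = 1.860, df 8, critical r = 0.55.

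An observed r of 0.5 is therefore significant at N = 20 and not at N = 10. Its 95% interval is tanh(0.549 ± 1.96/√(N − 3)): 0.07 to 0.77 at N = 20, and −0.19 to 0.86 at N = 10. Simulated one-sided power at a true r of 0.5 is about 75% against 46%.

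**3. Population, r_rm.** Error df = N(2 − 1) − 1 = N − 1.
- N = 20: df 19, t = 1.729, critical r_rm = 0.37.
- N = 10: df 9, t = 1.833, critical r_rm = 0.52.

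Simulated one-sided power at a true within-subject r of 0.5 is about 77% against 50%.

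**4. Tier.** The chance of at least one false positive among uncorrected, independent one-sided 0.05 tests is 1 − 0.95² = 9.75% with two and 1 − 0.95⁴ = 18.5% with four. The tests share subjects and will be correlated, which lowers both figures: at an assumed common correlation of 0.5 they are about 9% and 14%. The threshold of each single test is 0.05 under either label.

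**5. What r_rm measures.** With two sides, each side's deviation from the subject mean is plus or minus half the left-right difference d. Hence r_rm = Σ d_x d_y / √(Σ d_x² · Σ d_y²). Adding a constant to both sides of one patient leaves every d unchanged, so a patient's overall level of k_e or severity does not enter.

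Simulation at N = 20 used a between-subject r of 0.5 or 0.7 and a within-subject r of 0. The between-subject share s of each variable's variance was an assumption, 0.5 to 0.9. r_rm rejects in about 5% of trials, its null rate. The correlation of two-side means rejects in 43–71% (r = 0.5) and 69–96% (r = 0.7).

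These rates are below the 75% and 98% in step 1 because side-specific variation dilutes the correlation of the means to r · s/(s + (1 − s)/2). For r = 0.5 that is 0.5 × 0.5/0.75 = 0.33 at s = 0.5, and 0.5 × 0.9/0.95 = 0.47 at s = 0.9.

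**The case against.** The strongest reply is that this is a one-word slip. #1 to #4 form one list introduced by a paragraph about Aim 1 subjects, Specific Aim 1 names posterior putamen and asymmetry, and Aim 2 has its own before/after analysis. On that reading the N = 10 figures describe an analysis nobody intends. The slip is likely. The heading is still the operative label over these two tests, and following it would change the result at an observed r of 0.5.

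On tier, the reply is largely right about consequences. Each threshold stays at one-sided 0.05. The outlier rule describes the primary analyses as correlations of k_e with severity or duration, which fits #3 and #4 anyway. A subject without a k_e cannot enter any k_e correlation. The word exploratory may refer only to the later paragraph of secondary analyses. What stands is that two statements about the same four comparisons cannot both hold.

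On the estimator, the authors clearly know that r_rm is within-subject, since that is why they add a between-subject result. Asking for r and an interval is partly a reporting addition.

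A reader might infer that the cited table row is an invalid test, for example one of whether patients differ in level rather than whether k_e tracks severity. The documents do not support that. The table is not reproduced, and the row may be a correlation of subject averages, which would be sound.

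**Conclusion.** The plan is wrong as written on population and inconsistent on tier, and it leaves the between-subject estimate unspecified. The population error is the most consequential. Read literally, it raises the critical between-subject r from 0.38 to 0.55 and the critical r_rm from 0.37 to 0.52, and cuts power at a true r of 0.5 from about 75% to 46% and from 77% to 50%. These figures assume nominal sample sizes, normal data and the plan's r of 0.5. They make no allowance for a narrower severity range in the untreated group, because the documents give no figure for it.

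The tier conflict changes how a positive putamen result is described and how large the uncorrected primary family is (9.75% or 18.5% if independent). It does not change any test's threshold, and a reader should not infer that it does. Comparisons #1 and #2 keep their own population and estimator. The estimator point is an omission: r_rm cannot show whether worse patients have higher posterior putamen k_e, and the quantity that could show it is not written down.

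**What to change.** Three edits to the analysis plan, a few sentences in all, with no new data or procedures.

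1. In the heading over #3 and #4, change Aim 2 to Aim 1 and keep them secondary.
2. In Additional analysis details, change the count of numbered primary analyses from four to two, and state that the outlier and missing-k_e rules also cover #3 and #4. If the sponsor intends four primary tests, relabel #3 and #4 as primary in Data analysis instead.
3. Keep r_rm for left-right asymmetry and add, for example: *The between-subject association will be the Pearson correlation (Spearman under the outlier rule) of each subject's two-side mean posterior putamen k_e with the two-side mean off-period tapping speed or hemi-UPDRS, one point per subject, one-sided (negative for tapping, positive for UPDRS), reporting r, its 95% confidence interval and p.* If the cited row is already a correlation of subject averages, this only writes it down and adds r and its interval.

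One downside should be disclosed: two-side means absorb some within-subject association. With a within-subject r of 0.5 and a between-subject r of 0, the means correlate at 0.5 × ((1 − s)/2)/(s + (1 − s)/2), which is 0.17 at s = 0.5 and 0.27 at s = 0.3. Simulated one-sided rejection at N = 20 is about 6–17% at assumed shares of 0.5 to 0.9, and about 32% at 0.3. A random-intercept model with separate within and between slopes does not avoid this, because with two sides its between-slope test statistic is the same.
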